## 9.4 ANALYSIS PLAN

### 9.4.1 EFFICACY ANALYSES

Within each cohort, all participants who receive the protocol-specified booster dose of the Moderna COVID-19 vaccine and then have blood sampled within the protocol-specified time window will be included in the efficacy analysis ("efficacy analysis datasets"). There will be an efficacy dataset for each cohort individually.

For the primary and second secondary objectives, the response rate (RR), which is the primary endpoint, will be summarized with frequency, percentage and its associated 2-sided 90% confidence interval (i.e., 1-sided 95% confidence interval), separately by each cohort and by the combined cohort (Cohort 1+2).

For the second secondary objectives, the Fisher's exact test will be used to compare between Cohort 3 vs. Cohort 1+2.

For the third secondary objective, the patient demographic, clinical, and immune characteristics will be summarized by mean, median, standard deviation, range, confidence interval for continuous variables and by frequency, percentage and its associated confidence interval for categorical variables.

As an exploratory analysis, univariable logistic models will be used to explore the associations between patient characteristics and the treatment response.

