## 9.3 SAMPLE SIZE DETERMINATION

The specific hypothesis being tested is that it may be possible to induce a protective humoral immune response with a booster dose of the Moderna COVID-19 vaccine in patients with hematologic malignancies who did not have an adequate response to first vaccination with any of the available COVID-19 vaccines. The null hypothesis is that 5% or less of patients who have an anti-SARS-CoV2-IgG Ab titer of less than 2.0 S/CO will spontaneously develop a higher titer. We hypothesize that at least 15% of patients in each cohort will develop a titer of 2.0 S/CO or greater in response to the vaccine, without toxicity in excess of that previously described amongst COVID-19 vaccine recipients.

Thus, the sample size for each cohort of this trial was determined using the Phase 2 single-arm single-stage design based on the following statistical assumptions:  $p_0=5\%$ ,  $p_1=15\%$ , 1-sided alpha = 5%, and power = 80%. In this case, 52 patients would be enrolled to each of the three cohorts. In each cohort, at least 6 patients would need to develop an anti-SARS-CoV2-IgG Ab titer of  $>2.0$  S/CO to reject the null hypothesis. Therefore, a total of 156 response-evaluable patients would be enrolled in this 3-parallel cohort, single-arm, single-stage Phase 2 trial. Given that the study intervention is a single vaccination, and the primary endpoint requires a single visit for a physical a blood sample collection, there should be relatively few non-evaluable patients. Patients who are non-evaluable for the primary endpoint will be replaced only if it becomes evident that this is needed to determine whether or not the primary endpoint is met in any/all of the cohort(s). We expect this will amount to no more than 5 additional patients in any of the three cohorts, so the maximum number of enrolled participants is 171 (= 57 x 3 cohorts).

The size of the trial will also permit a comparison of the likelihood of developing a strong positive response amongst the pooled participants form Cohorts 1 and 2 (i.e., the participants with NO RESPONSE to prior vaccination) versus the participants in Cohort 3 (i.e., the patients who had a WEAK POSITIVE RESPONSE to prior vaccine) as the second secondary objective. We hypothesize that the absolute difference in response rate between Cohort 3 vs. Cohort 1+2 is 20% or more against the response rate of 15% in Cohort 1+2 (i.e., Cohort 3: 35% vs. Cohort 1+2: 15%). The sample sizes of 156

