(Cohort 3: 52 vs. Cohort 1+2: 104) will achieve 82.7% power to detect a difference of 20% between two groups at a 1-sided 5% level when the Fisher's exact test is used.

Each cohort in the primary object will be tested at a 1-sided 5% level and the second secondary objective will be also evaluated at a 1-sided 5% level. No correction for multiple comparison is planned between these primary and second secondary objectives

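### For the Cohort 3 versus Cohorts 1+2 comparison, Fisher's exact test is valid but uses only about 3.1–3.5% of its one-sided 5% level; Boschloo's exact test would add 2 to 4 points of power with the same patients.

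*Combined protocol and SAP*

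**What the plan says.** Section 9.3 introduces a comparison of Cohort 3 (weak positive response to prior vaccination) with pooled Cohorts 1 and 2 (no response) "as the second secondary objective". The group sizes are "Cohort 3: 52 vs. Cohort 1+2: 104". The planning alternative is a response rate of 35% in Cohort 3 against 15% in the pooled group. The design "will achieve 82.7% power to detect a difference of 20% between two groups at a 1-sided 5% level when the Fisher's exact test is used". The level is repeated at the end of the section: "the second secondary objective will be also evaluated at a 1-sided 5% level". On multiplicity it adds: "No correction for multiple comparison is planned between these primary and second secondary objectives".

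Section 9.4.1 names the same test for the analysis: "the Fisher's exact test will be used to compare between Cohort 3 vs. Cohort 1+2". Design and analysis therefore agree. Neither section mentions the actual size of Fisher's test at these sample sizes, or an unconditional exact alternative.

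**The concern.** Fisher's test conditions on the total number of responders in both groups. This design fixes target group sizes but not that total. Conditioning makes the p-value discrete and coarse, so the test usually rejects less often under the null than its nominal level allows. The plan grants this comparison a 5% one-sided error rate; a test that spends appreciably less gives up some power for no gain in validity.

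This is the only formal between-group test in the plan (the univariable logistic models in section 9.4.1 are exploratory), and the only objective beyond the primary for which power is given. At stake is a modest amount of power and the reading of borderline results: some outcomes that a valid exact 5% test would reject are declared negative. The primary inference, a single-arm test in each cohort, is not involved.

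**Working it through.** **Inputs.** From sections 9.3 and 9.4.1: n₃ = 52, n₁₂ = 104, one-sided α = 0.05, Fisher's exact test, alternative 35% vs 15%, stated power 82.7%. The 52 per cohort are described as response-evaluable, so no dropout adjustment is applied.

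**Step 1: the stated power.** For each of the 53 × 105 = 5,565 possible outcomes (x responders of 52, y of 104), the one-sided Fisher p-value is P(X ≥ x), where X is hypergeometric with population 156, x + y responders and 52 drawn. Power is the sum of Bin(x; 52, 0.35) × Bin(y; 104, 0.15) over outcomes with p ≤ 0.05.

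- Exact Fisher power: 83.3%.
- Normal approximation with continuity correction: pooled rate (52 × 0.35 + 104 × 0.15)/156 = 0.2167; null SE = √(0.2167 × 0.7833 × (1/52 + 1/104)) = 0.0700; alternative SE = √(0.35 × 0.65/52 + 0.15 × 0.85/104) = 0.0748; correction = ½(1/52 + 1/104) = 0.0144. Power = Φ((0.20 − 0.0144 − 1.645 × 0.0700)/0.0748) = Φ(0.94) = 82.7%.

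The continuity-corrected formula matches the plan's figure and is probably what was used. The uncorrected formula gives 87.2%. The stated power is met, and slightly understated.

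**Step 2: actual size of Fisher's test.** The same sum with a common rate p in both groups gives the Fisher row in the table below. The maximum over all p is 3.75%.

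**Step 3: Boschloo's test.** It uses the Fisher p-value as its statistic and rejects when that value is at or below a cut-off c. Here c is the largest value for which the rejection probability, maximised over the common rate (1,999-point grid from 0.0005 to 0.9995), stays at or below 5%. This gives c ≈ 0.063 and a maximum size of 4.88%. Since c exceeds 0.05, every outcome that Fisher's test rejects is also rejected; 39 further outcomes are added and none is lost. Power therefore cannot be lower at any pair of true rates.

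| Common rate | 15% | 20% | 25% | Maximum |
|---|---|---|---|---|
| Fisher size | 3.1% | 3.4% | 3.5% | 3.75% |
| Boschloo size | 3.9% | 4.3% | 4.4% | 4.88% |

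**Step 4: power with the same patients.**

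| Cohort 3 vs Cohorts 1+2 | Fisher | Boschloo | Gain (points) |
|---|---|---|---|
| 35% vs 15% (plan) | 83.3% | 85.7% | 2.4 |
| 30% vs 15% | 63.0% | 66.8% | 3.8 |
| 40% vs 20% | 79.0% | 81.8% | 2.8 |
| 50% vs 30% | 73.5% | 77.0% | 3.5 |
| 30% vs 10% | 88.3% | 90.2% | 1.9 |

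Only the first row is the plan's scenario; the others are assumptions to show the range.

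**Step 5: what the gain is worth in patients.** For Fisher's test to reach 85.7% at 35% vs 15%, about 57 vs 114 are needed (86.1%; 56 vs 112 gives 85.3%). That is 171 − 156 = 15 more evaluable patients, equal to the plan's whole enrolment cap of 171.

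**Step 6: an outcome on which the tests differ.** With 13/52 (25.0%) vs 14/104 (13.5%), Fisher's p is 0.060 and Boschloo's p is 0.044.

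**The case against.** The strongest reply is that nothing needs fixing. Fisher's test is valid; a 5% level is a ceiling, not a quota; and the power was stated for Fisher's test, so its conservatism is already paid for and power still exceeds 80%. All of that stands. A reader might infer from the sizes in the table that the plan's power claim is wrong or that its test is invalid. The documents support neither: the test is named consistently in both sections, and the exact power is slightly above the stated figure.

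A reader might also infer that Boschloo's test reclaims the full 5%. It does not. At a common rate of 15% it recovers 3.9 − 3.1 = 0.8 of the 5 − 3.1 = 1.9 unused points, less than half.

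Nor is the switch free. The actual false-positive rate rises, for example from 3.1% to 3.9% at a common rate of 15%, in a plan with no multiplicity correction between the primary and second secondary objectives. The rate nevertheless stays within the level the plan itself allots.

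It would also be an over-reading to treat this as the trial's key comparison. The plan calls it the second secondary objective.

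Finally, the benefit is small: under the planned alternative the tests disagree in about 1 trial in 40, and the 13/52 vs 14/104 example is one of 39 such outcomes among 5,565, with an observed difference (11.5 points) well below the hypothesised 20. The groups are also not randomised, which bears more on the meaning of the result than this choice does. These points limit the weight of the suggestion. They do not remove the fact that a test with power at least as high at every pair of rates is available at the same nominal level.

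**Conclusion.** A cheap improvement, not an error. At 52 vs 104 Fisher's one-sided 5% test has an actual size of 3.1–3.5% for common rates of 15–25% and at most 3.75%. Boschloo's test has a maximum size of 4.88%, is never less powerful, and gains 2.4 points at the planned alternative (83.3% to 85.7%) and roughly 2 to 4 points in the scenarios examined.

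The figures assume exactly 52 and 104 evaluable patients, independent binomial responses, and a single common rate across the pooled Cohorts 1 and 2. They will shift somewhat if the evaluable numbers differ. Keeping Fisher's test would be defensible. The primary single-arm tests are unaffected.

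**What to change.** Before any outcome data are seen:

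- In sections 9.3 and 9.4.1, name Boschloo's exact unconditional test, one-sided 5%, in place of Fisher's for Cohort 3 versus Cohorts 1+2, computed on the evaluable numbers actually obtained.
- In section 9.3, restate the power as 85.7% for 35% vs 15% with 52 vs 104.
- Report the Fisher p-value alongside as descriptive, and say that the decision rests on Boschloo's test.

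The timing matters: changing the test after seeing a Fisher p-value between 0.05 and 0.063 would not be credible.

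The cost is a short wording change in two sections and the use of standard software, with no extra patients. The downsides are that readers know the test less well and that the actual type I error is slightly higher than Fisher's, though still within 5%.

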### 2.2 BACKGROUND

As of June 2021, there have been over 33,000,000 SARS-CoV2 infections in the United States, with over 600,000 deaths (REF 1). Further, many survivors of the infection suffer with long-term symptoms or complications. Three different SARS-CoV2 vaccines have been authorized by the FDA for emergency use to prevent SARS-CoV2 infections: the Pfizer-BioNTech COVID-19 vaccine, the Moderna COVID-19 vaccine, and the Janssen (Johnson & Johnson) COVID-19 vaccine. The Pfizer and Moderna products are mRNA vaccines with approximately 95% efficacy in preventing SARS-CoV2 infections in patients who are not immunocompromised (REFS 2 and 3). The safety and immunogenicity of the Moderna vaccine in immunocompetent older adults appears to be similar to that observed in younger adults (REF 4). That said, it has been clearly demonstrated that individuals with compromised immune systems are less likely to mount a protective humoral immune response to any of the available SARS-CoV2 vaccines. This includes patients with hematologic malignancies. For example, in a series of 92 multiple myeloma (MM) patients who had received first vaccination with either the Pfizer or AstraZeneca COVID-19 vaccines, 30% failed to mount any measurable immune response (REF 5). Other investigators have corroborated these findings in a series of vaccinated patients with MM or myeloproliferative diseases (REF 6). In the latter report, patient age as well as treatment history were also associated with the likelihood of vaccine responsiveness. The list of potential interventions to address inadequate humoral immune response to first SARS-CoV2 vaccination includes administration of booster dose(s) with any of the available vaccines. In this trial, we will specifically evaluate the efficacy and safety of administering booster dose(s) of the Moderna mRNA vaccine to patients with MM, AL amyloidosis, or other hematologic malignancies who did not have an adequate humoral immune response after first vaccination with any of the available COVID-19 vaccines.

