## 4 STUDY DESIGN

### 4.1 OVERALL DESIGN

The specific hypothesis being tested is that it may be possible to induce a protective humoral immune response with a booster dose of the Moderna COVID-19 vaccine in patients with hematologic malignancies who did not have an adequate response to first vaccination with any of the available COVID-19 vaccines. To test this hypothesis, the Karmanos Cancer Institute will conduct a Phase II single-stage trial in which patients with a negative or weak positive anti-SARS-CoV2 IgG antibody test (defined as <1.00 S/CO and 1.00-1.99 S/CO, respectively) will receive a single standard dose of the Moderna COVID-19 vaccine intramuscularly, and then have anti-SARS-CoV2 IgG antibody levels checked 28 days (+/-3 days) later. This will be a single institution trial which will be open to enrollment at the Detroit (Dresner) and Farmington Hills (Weisberg) treatment facilities. As this is an open label Phase 2 trial, there is no randomization or stratification involved. There will be three cohorts enrolled: a cohort of MM and AL amyloidosis patients with an anti-SARS-CoV2-IgG Ab level of <1.0 S/CO, a cohort of patients with other hematologic malignancies (HM) with an anti-SARS-CoV2-IgG Ab level of <1.0 S/CO and a mixed MM/AL/HM cohort in which patients have an anti-SARS-CoV2-IgG Ab level of 1.0-1.99 S/CO ("low-positive cohort"). Each cohort will be of sufficient size to evaluate the efficacy of the intervention separately, and all secondary endpoints will be analyzed on the entire combined patient set.

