### 5 STUDY POPULATION

#### 5.1 INCLUSION CRITERIA

In order to be eligible to participate in this study, an individual must meet all of the following criteria:

1. Provision of signed and dated informed consent form
2. Stated willingness to comply with all study procedures and availability for the duration of the study
3. Male or female, aged 18 years of age or older
4. Previously diagnosed with MM/AL amyloidosis (Cohorts 1 or 3) or other hematologic malignancy (Cohorts 2 or 3).
5. Previously received any one of the available COVID-19 vaccines (between 4 and 36 weeks prior to enrollment)
6. Anti-SARS-CoV2 IgG antibody titer of results less than 1.0 units (Cohorts 1 and 2), or 1.0-1.99 units (Cohort 3). Antibody titers will be measured within 14 days of enrollment.
7. If currently receiving potentially immunosuppressive anti-neoplastic therapy for their underlying hematologic condition, a two-week interruption in therapy before and after the booster dose of vaccine is ENCOURAGED BUT NOT REQUIRED (physician discretion).

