### 8.2 SAFETY AND OTHER ASSESSMENTS

Safety Assessments: participants will have a medical history, vitals, and physical exam and bloodwork for laboratory testing including cardiac biomarkers performed during screening and on day 28 (+/- 3 days). Participants will also be contacted by phone/text/email/video platform on days 2-8, 15, and 22 to document any AEs experienced. Any patients reporting chest pain, palpitations, shortness of breath, or other symptoms which in the opinion of the treating physician suggest cardiac etiology will be asked to have additional bloodwork done to measure cardiac biomarkers (hsTrop I, BNP).

**Baseline Patient characteristics:** The patient's chart in the EMR will be accessed to document general demographics, their hematologic diagnosis and the status of that disease, current and past treatment history for the underlying hematologic condition, other past medical history, medications, and baseline laboratory parameters (including but not limited to neutrophil count, lymphocyte count, immunoglobulin levels). These and other variables (TBD) will be entered into a CRF to be used for eventual univariate and multivariate analyses. Health Insurance Portability and Accountability Act (HIPAA) rules, other relevant federal or state laws, and local institutional requirements will be followed, as applicable.

Blood sample collection for future correlative testing (e.g., immune cell profiling, assessment of immune exhaustion, etc). The following samples will be collected and stored in [name]'s laboratory: **one 15 mL EDTA tube of peripheral blood** obtained prior to administration of the booster dose, and **a second 15 mL EDTA tube of peripheral blood obtained at the day 28 visit**. The first correlative testing we are planning to perform is a detailed anti-viral protein antibody evaluation using the Bio-Plex Pro SARS-CoV-2 Serology assay. This assay is a sensitive and specific method to monitor the antibody immune response profile against viral proteins. There are three isotype-specific 4-plex panels that measure antibodies against SARS-CoV-2 Nucleocapsid, Receptor Binding Domain, Spike 1, and Spike 2 viral proteins. The isotype-specific antibodies detected are IgA, IgG, and IgM. The viral-protein-coated beads can be used to assay antibodies in multiple species and only need to be paired with a species-specific biotinylated

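### Objective 2 has conflicting response definitions, one of which Cohort 3 cannot meet; its unstratified Fisher test would also benefit from a prespecified disease-stratified sensitivity analysis.

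*Combined protocol and SAP*

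**What the plan says.** **Response definition.** Five places bear on objective 2.

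- Synopsis, secondary endpoint 2: the rate of IgG seroconversion, spelled out as going from negative to positive.
- Section 3, endpoint table: humoral immune responses at day 28, with no cut-off.
- Section 9.2: the primary and second secondary endpoints share one seroconversion rate, glossed as positive versus negative.
- Section 9.3: the trial size will "permit a comparison of the likelihood of developing a strong positive response amongst the pooled participants form Cohorts 1 and 2" versus Cohort 3. The hypothesis counts titres at or above 2.0 S/CO; the decision rule counts titres strictly above 2.0.
- Section 9.4.1: the response rate is simply called the primary endpoint, which leads back to the Synopsis wording.

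Section 4.1 enrols "patients with a negative or weak positive anti-SARS-CoV2 IgG antibody test (defined as <1.00 S/CO and 1.00-1.99 S/CO, respectively"), and Cohort 3 is the weak positive group.

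**Comparison.** Section 9.3 states that 52 versus 104 patients "will achieve 82.7% power to detect a difference of 20% between two groups at a 1-sided 5% level", from 35% versus 15%. Section 9.4.1 says the "exact test will be used to compare between Cohort 3 vs. Cohort 1+2".

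**Disease.** Eligibility reads "Previously diagnosed with MM/AL amyloidosis (Cohorts 1 or 3) or other hematologic malignancy (Cohorts 2 or 3"). Cohorts 1 and 2 are therefore each one disease group with a target of 52, while Cohort 3 is "a mixed MM/AL/HM cohort in which patients have an anti-SARS-CoV2-IgG Ab level of 1.0-1.99 S/CO", with no quota. Section 9.4.1 reports Cohorts 1 and 2 separately but does not split Cohort 3 by disease, and its only models are exploratory and univariable. Section 8.2 says baseline variables "will be entered into a CRF to be used for eventual univariate and multivariate analyses", without naming a model.

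**The concern.** Objective 2 is the only secondary comparison with a power statement, so its endpoint has to be one that both groups can meet and neither meets at entry. On the Synopsis wording the Cohort 3 rate is zero by definition. On the section 9.2 wording Cohort 3 may count as positive before the booster is given. An analyst following either would answer a different question from the one that was powered.

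The disease point is secondary. The plan separates MM/AL from other malignancies for its primary tests, then pools them in this comparison against a cohort whose mix is left to accrual. If the mix differs and disease affects response, part of an observed difference could reflect which diseases filled Cohort 3, or a real difference could be hidden. The plan specifies no analysis to tell these apart.

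**Working it through.** **1. Definitions applied to Cohort 3 (entry titre 1.0-1.99 S/CO)**

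| Source | Rule | Consequence for Cohort 3 |
|---|---|---|
| Synopsis | negative to positive | No one starts below 1.00, so 0/52 |
| Section 9.2 | positive versus negative | If positive means at least 1.0, all 52 are positive at entry |
| Section 3 | no cut-off | Undefined |
| Section 9.3 | 2.0 S/CO line | Can be met or missed; 35% is possible |

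Only the last row fits the powered 35% versus 15%. Within section 9.3, a titre of exactly 2.0 is a response under the hypothesis but not under the decision rule.

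**2. The plan's power figure**

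Inputs from section 9.3: 52 at 35%, 104 at 15%, one-sided 5%.

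Continuity-corrected normal approximation:
- Pooled rate = (52×0.35 + 104×0.15)/156 = 0.2167
- Null SE = √[0.2167×0.7833×(1/52 + 1/104)] = 0.0700
- Alternative SE = √[0.35×0.65/52 + 0.15×0.85/104] = 0.0748
- Correction = ½(1/52 + 1/104) = 0.0144
- z = (0.20 − 0.0144 − 1.645×0.0700)/0.0748 = 0.94, so power = 82.7%

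Full enumeration of Fisher's test over all 53 × 105 tables gives 83.3%, with true size 3.1% at 15% versus 15%. The stated figure is right.

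**3. Effect of disease mix with no prior-response effect**

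Let m of the 52 Cohort 3 patients have MM/AL, with response rates p_M (MM/AL) and p_H (other) that do not depend on prior response. The crude difference is then (m/52 − ½)(p_M − p_H). The documents give neither m nor rates by disease. The assumed pairs 20/10% and 25/5% both average the planned 15%. The stratified exact test sums Cohort 3 responders over the two disease strata and refers the sum to the convolution of two hypergeometric distributions, conditional on stratum totals. All entries are enumerated.

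| m | Rates | Crude difference | Fisher rejects | Stratified rejects |
|---|---|---|---|---|
| 26 | 20/10 | 0 | 3.0% | 3.1% |
| 26 | 25/5 | 0 | 2.6% | 3.1% |
| 36 | 20/10 | 1.9 points | 5.9% | 3.1% |
| 36 | 25/5 | 3.8 points | 10.0% | 3.1% |
| 47 | 20/10 | 4.0 points | 11.2% | 3.1% |
| 47 | 25/5 | 8.1 points | 26.7% | 3.2% |

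With 15% in both diseases, Fisher rejects 3.1% at every mix.

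**4. Opposite imbalance**

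With m = 16 and a true +20 points within each disease, Fisher has 76.7% power against 83.3% stratified (base 20/10%), or 68.9% against 86.5% (base 25/5%). Only the stratified test is significant in about 7% and 17.5% of trials respectively.

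**5. Price of stratifying when it is not needed (35% versus 15% in both diseases)**

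| m | Fisher | Stratified |
|---|---|---|
| 26 | 83% | 83% |
| 36 | 83% | 82% |
| 42 | 83% | 79% |
| 47 | 83% | 76% |
| 52 | 83% | 70% |

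**The case against.** On the endpoint, one can say that section 9.3 makes the intent clear: nobody plans for 35% in Cohort 3 under a rule that forces zero. That is fair, and a reader should not infer that objective 2 is bound to fail in practice. But section 9.4.1 points back to the primary endpoint rather than to section 9.3, and section 9.3 itself uses two versions of the cut-off.

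On disease mix, the opposing case is stronger. The objective asks whether weak positive patients respond more often than non-responders, and Fisher is valid for that plain comparison. Neither condition for distortion is documented: section 9.3 uses the same 15% for every cohort, and section 2.2 reports that "patient age as well as treatment history were also associated with the likelihood of vaccine responsiveness", not disease group. Section 3 says only that disease-related factors may matter. Reporting Cohorts 1 and 2 separately already shows any disease difference among non-responders, and section 8.2 anticipates multivariate work. If disease does not matter, stratifying can only cost power. All of this stands. It supports a sensitivity analysis, not replacement of the planned test.

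Two stronger inferences are tempting. One is that the Fisher test or its power is wrong; both check out. The other is that Cohort 3's starting point nearer 2.0 confounds the comparison; being nearer is part of what weak positive means, and section 9.3 asks about reaching a strong positive response from that state.

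**Conclusion.** The endpoint wording for objective 2 is wrong as written, and this rests on no assumption: one definition gives Cohort 3 0/52, another may count it as positive at baseline, and only the 2.0 S/CO line is compatible with the power calculation.

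The disease-mix point is a low-cost improvement. Its size rests on assumed rates and mixes. At rates averaging 15%, Fisher's rejection without a prior-response effect is 5.9% or 10.0% at 36/52 MM/AL, and 11.2% or 26.7% at 47/52. The spurious difference is at most 8.1 points in these cases, against the planned 20. A reader might infer that the comparison is biased; the documents support only that it could be, and not if Cohort 3 is near 50:50 or response is alike across diseases. The 52:52 comparator is itself a target, since up to 57 may be enrolled per cohort. The primary cohort-wise tests are untouched by the mix question.

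**What to change.** 1. **One response definition.** State the same rule, based on the 2.0 S/CO line, in the Synopsis, section 3 and sections 9.2, 9.3 and 9.4.1. Choose either at-or-above 2.0 or strictly above 2.0 and use it throughout.

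2. **Sensitivity analysis in section 9.4.1.** Keep Fisher as the test of objective 2. Report Cohort 3 response separately for MM/AL and other malignancy. Prespecify a one-sided 5% exact test stratified on that factor, labelled as a sensitivity analysis.

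3. **Discordant results, fixed in advance.** If only Fisher is significant, disease mix may explain the difference. If only the stratified test is significant, objective 2 is not met by its planned test; disease mix may have masked a difference, and the result is supportive only.

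4. **Conclusion.** Word it as an association. Two strata leave age, treatment history and time since vaccination (4 to 36 weeks under section 5.1) unadjusted.

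The cost is protocol wording; diagnosis and both titres are already collected. Fisher's power is unchanged. The sensitivity test is weaker when Cohort 3 is unbalanced, falling from 83% to 70% if Cohort 3 is all one disease, so its non-significance should not be read as refuting a significant Fisher result.

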##### 9.1.2 SECONDARY OBJECTIVES

1. To determine whether booster dosing with the Moderna COVID-19 vaccine is safe in patients with multiple myeloma, AL amyloidosis, or other hematologic malignancies.
2. To compare the humoral immune responses between the patients who had a WEAK POSITIVE RESPONSE to prior vaccine (Cohort 3) vs. those with NO RESPONSE to prior vaccination (Cohorts 1 and 2).

3. To descriptively summarize clinical and immune characteristics which contribute to likelihood of responding to booster dosing with the Moderna COVID-19 vaccine.

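### The exploratory logistic models have no term for prior response, so on pooled cohorts a strongly imbalanced characteristic can look associated with response when it has no effect

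*Combined protocol and SAP*

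**What the plan says.** The third secondary objective (section 9.1.2) is "To descriptively summarize clinical and immune characteristics which contribute to likelihood of responding to booster dosing". Section 9.4.1 serves it with summary statistics, then adds as exploratory that "univariable logistic models will be used to explore the associations between patient characteristics and the treatment response". It gives no covariate, stratification or dataset for these models.

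Three other statements bear on how the models would be run:

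- Section 4.1: "all secondary endpoints will be analyzed on the entire combined patient set".
- Section 9.4.1, before the models are mentioned: "There will be an efficacy dataset for each cohort individually". Response is also to be summarised for Cohorts 1+2 together. The only all-cohort dataset that section 9.4 defines is the toxicity one (9.4.2).
- Section 8.2: baseline variables are recorded "to be used for eventual univariate and multivariate analyses". Section 9 specifies no multivariable model.

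Under section 5.1, Cohorts 1 and 2 have a screening titre below 1.0 and Cohort 3 has 1.0-1.99. Cohort 1 is all myeloma or amyloidosis (MM/AL), Cohort 2 is all other malignancies, and Cohort 3 is a mixture. Section 9.3 treats a titre of 2.0 S/CO as the response threshold and assumes 35% response in Cohort 3 against 15% in Cohorts 1+2.

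**The concern.** If all three cohorts enter one model, prior-response group is a candidate confounder that the design itself creates. It separates patients by screening titre, and the plan expects it to carry a large difference in response. With the 2.0 S/CO threshold of section 9.3, Cohort 3 starts closer to the target on the same scale. Diagnosis is tied to cohort, and immunoparesis or treatment history could plausibly differ between patients with no response and those with a weak response to earlier vaccination.

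A model with one characteristic and nothing else then mixes that characteristic's own association with the difference between groups. The risk is that the trial reports as a clinical or immune predictor something that only marks membership of Cohort 3.

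**Working it through.** **Inputs.** From section 9.3: 52 patients in Cohort 3 at 35% response, and 104 in Cohorts 1+2 at 15%. The documents give no prevalences for any characteristic, so those below are assumptions shown over a range.

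**1. The plan's own figure.** Section 9.3 states 82.7% power for the one-sided 5% Fisher test of 35% against 15%. Summing Binomial(52, 0.35) × Binomial(104, 0.15) over all outcomes with Fisher p ≤ 0.05 gives 83.3%, so the figure is closely reproduced. The same rates imply a group odds ratio (OR) of (0.35/0.65)/(0.15/0.85) = 3.05. Expected responders are 52 × 0.35 + 104 × 0.15 = 33.8 of 156.

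**2. Spurious odds ratio.** Take a binary characteristic with prevalence a in Cohort 3 and b in Cohorts 1+2, and no effect within either group. Pooled response rates are:

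- with it: (52a × 0.35 + 104b × 0.15)/(52a + 104b)
- without it: the same expression with 1−a and 1−b in place of a and b.

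Example, a = 60% and b = 30%:

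- with: (31.2 × 0.35 + 31.2 × 0.15)/62.4 = 0.250
- without: (20.8 × 0.35 + 72.8 × 0.15)/93.6 = 0.194
- crude OR: (0.250/0.750)/(0.194/0.806) = 1.38, where the true within-group value is 1.

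**3. False positives.** 100,000 simulated trials per row compared the pooled univariable likelihood-ratio test with a Cochran-Mantel-Haenszel test stratified by Cohort 3 versus 1+2, both two-sided 5%.

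| Prevalence, Cohort 3 / 1+2 | Crude OR | Univariable | Stratified |
|---|---|---|---|
| 50 / 50% | 1.00 | 5.1% | 4.9% |
| 50 / 40% | 1.11 | 5.9% | 4.9% |
| 50 / 30% | 1.25 | 8.9% | 5.0% |
| 60 / 30% | 1.38 | 13.1% | 4.9% |
| 70 / 30% | 1.53 | 19.3% | 4.9% |
| 80 / 20% | 1.90 | 37.6% | 4.9% |

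A smaller run (1,500 trials each) used logistic models with the imbalance in the other direction. For Cohort 3 / 1+2 prevalences of 50/60%, 40/70%, 30/70% and 30/80%, the univariable false-positive rates were 5%, 14%, 19% and 29%. With a two-level group term they were 4.5-5.5%.

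**4. Diagnosis.** With 52 patients each in Cohorts 1 and 2, MM/AL is 50% of Cohorts 1+2 by design. If its share of Cohort 3 is 30%, 70% or 80%, the crude OR is 0.81, 1.24 or 1.40, with false positives of 8.7%, 8.6% or 13.5%. At 50% there is no bias.

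**5. Dependence on the response difference.** At 60/30% prevalence, Cohort 3 response of 25%, 35%, 50% or 70% gives crude ORs of 1.20, 1.38, 1.63 or 1.98 and false positives of 7.4%, about 13%, 27.2% or 50.9%. If both groups respond at 15%, even 70/30% gives OR 1.00 and 5.3%.

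**6. Cost of adjusting.** A two-level group term raises the standard error of the characteristic by about 4-19% across the logistic scenarios. A three-level cohort term behaves differently for diagnosis, which is fixed within Cohorts 1 and 2, so that only Cohort 3's 52 patients inform it. Assuming 50% MM/AL in Cohort 3, the median standard error rises from 0.39 to 0.60 (0.60/0.39 = 1.54), against 0.41 with the two-level term.

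**The case against.** The strongest reply is that the plan does not say these models are pooled. The sentence names no dataset, the same section defines datasets by cohort, and section 4.1 speaks of secondary endpoints whereas these models are labelled exploratory. Fitting by cohort would remove the between-cohort confounding. This stands: pooling is an inference from 4.1. But fitting by cohort would sit badly with 4.1 and leave about 52 × 0.15 = 7.8 expected responders in each of Cohorts 1 and 2. Either way the dataset must be named.

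The objective is descriptive, and no alpha, power or decision attaches to the models. That limits the weight of the point, but it does not justify leaving in a foreseeable bias that is cheap to remove.

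Three stronger readings are tempting, and the documents do not support them:

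- *Every pooled association is confounded.* Bias needs both imbalance and a difference in response. It is negligible at 10 points, no document gives prevalences, and the 35% is a planning hypothesis.
- *These models are the trial's only inferential evidence on who responds.* The Fisher test compares prior-response groups directly, and response is reported by cohort. Cohort or titre could also be entered as a single predictor, although that would not adjust the other estimates.
- *Baseline titre drives response by construction.* That rests on the 2.0 S/CO threshold of section 9.3. Sections 3 and 9.2 word the endpoint as seroconversion, negative to positive, which does not fit Cohort 3.

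Adjustment also has a price in interpretation. Immunoparesis, for example, may act through low baseline titre, and conditioning on titre or group would then remove part of the association of interest. That is a good reason to show both estimates.

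**Conclusion.** The point holds as a modest one. The models are specified without adjustment, and section 4.1 points to the combined set. Under the plan's own 35% against 15%, a null characteristic imbalanced by 30-50 percentage points between Cohort 3 and Cohorts 1+2 would be flagged in about 13-30% of trials instead of 5%. At 10 points the rate is about 5-6%. These sizes rest on assumed prevalences, a binary characteristic, pooling of all 156 patients and the planned response rates. They fall to nominal if the groups respond alike, and grow if Cohort 3 responds better than planned. The primary cohort tests and the Fisher comparison are untouched.

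**What to change.** In section 9.4.1:

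- State that the exploratory models use the combined efficacy set, defined as the three cohort efficacy datasets together.
- Fit each characteristic with one prior-response term: either the two-level indicator Cohort 3 versus Cohorts 1+2 (or stratification by it), or continuous screening titre. Do not use three-level cohort plus titre. Cohort 3 versus 1+2 is itself a cut of titre, and the three-level term strips most of the information on diagnosis. The corrected error rates above are for the two-level term; a continuous titre term depends in addition on its functional form.
- Report adjusted odds ratios beside unadjusted ones, with a note that adjustment may remove part of the association for characteristics acting through low baseline titre.
- State the response cut-off that the models use (section 9.3 uses 2.0 S/CO).
- Reconcile section 4.1 (combined set), section 8.2 (univariate and multivariate) and section 9.4.1 (univariable, datasets by cohort).

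The cost is wording only. Screening titre is an eligibility measurement, so it is held for every participant, and about 34 expected responders support one extra term. The price is standard errors about 4-19% larger.
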